#### **1.2.1.2     *Rationale for Dose Selection/Regimen/Modification***

##### **a) Dose of Pembrolizumab:**

An open-label Phase I trial (Protocol 001) is being conducted to evaluate the safety and clinical activity of single agent pembrolizumab. The dose escalation portion of this trial evaluated three dose levels, 1 mg/kg, 3 mg/kg, and 10 mg/kg, administered every 2 weeks (Q2W) in subjects with advanced solid tumors. All three dose levels were well tolerated and no dose-limiting toxicities were observed. This first in-human study of pembrolizumab showed evidence of target engagement and objective evidence of tumor size reduction at all dose levels (1 mg/kg, 3 mg/kg and 10 mg/kg Q2W). No MTD has been identified to date. The highest dose tested in PN001 (10.0 mg/kg Q2W) will be the dose and schedule utilized in Cohorts A, B, C and D of this protocol to test for initial tumor activity. Recent data from other clinical studies within the pembrolizumab program has shown that a lower dose of pembrolizumab and a less frequent schedule may be sufficient for target engagement and clinical activity.

PK data analysis of pembrolizumab administered Q2W and Q3W showed slow systemic clearance, limited volume of distribution, and a long half-life (refer to IB). Pharmacodynamic data (IL-2 release assay) suggested that peripheral target engagement is durable (>21 days). This early PK and pharmacodynamic data provides scientific rationale for testing a Q2W and Q3W dosing schedule.

A population pharmacokinetic analysis has been performed using serum concentration time data from 476 patients. Within the resulting population PK model, clearance and volume parameters of pembrolizumab were found to be dependent on body weight. The relationship between clearance and body weight, with an allometric exponent of 0.59, is within the range observed for other antibodies and would support both body weight normalized dosing or a fixed dose across all body weights. Pembrolizumab has been found to have a wide therapeutic range based on the melanoma indication. The differences in exposure for a 200 mg fixed dose regimen relative to a 2 mg/kg Q3W body weight based regimen are anticipated to remain well within the established exposure margins of 0.5 – 5.0 for pembrolizumab in the melanoma indication. The exposure margins are based on the notion of similar efficacy and safety in melanoma at 10 mg/kg Q3W vs. the proposed dose regimen of 2 mg/kg Q3W (i.e. 5-fold higher dose and exposure). The population PK evaluation revealed that there was no significant impact of tumor burden on

exposure. In addition, exposure was similar between the NSCLC and melanoma indications. Therefore, there are no anticipated changes in exposure between different indication settings.

The rationale for further exploration of 2 mg/kg and comparable doses of pembrolizumab in solid tumors is based on (1) similar efficacy and safety of pembrolizumab when dosed at either 2 mg/kg or 10 mg/kg Q3W in melanoma patients, (2) the flat exposure-response relationships of pembrolizumab for both efficacy and safety in the dose ranges of 2 mg/kg Q3W to 10 mg/kg Q3W, (3) the lack of effect of tumor burden or indication on distribution behavior of pembrolizumab (as assessed by the population PK model), and (4) the assumption that the dynamics of pembrolizumab target engagement will not vary meaningfully with tumor type.

The choice of the 200 mg Q3W as an appropriate dose for the switch to fixed dosing is based on simulations performed using the population PK model of pembrolizumab showing that the fixed dose of 200 mg every 3 weeks will provide exposures that (1) are optimally consistent with those obtained with the 2 mg/kg dose every 3 weeks, (2) will maintain individual patient exposures in the exposure range established in melanoma as associated with maximal efficacy response, and (3) will maintain individual patients exposure in the exposure range established in melanoma that are well tolerated and safe.

A fixed dose regimen will simplify the dosing regimen to be more convenient for physicians and to reduce potential for dosing errors. A fixed dosing scheme will also reduce complexity in the logistical chain at treatment facilities and reduce wastage.

**b) Dose of Radiation and Choice of Modality:**

Most patients with metastatic NSCLC requiring palliative radiation receive 8 Gy SFRT or 20 Gy in 5 fractions. Several randomized controlled trials demonstrated that a single fraction of radiotherapy (8 Gy) is equivalent in palliation, and local control in comparison to a longer course of radiotherapy in patients with bone metastases. (41, 42) Similarly even in patients with lung or other visceral metastases no significant difference in symptom palliation and overall survival were noted with single fraction versus multiple fractions of radiation. (43) Moreover, SFRT is cost effective and prevents delays to initiation of systemic therapy. Animal studies suggest that low dose (2–4 Gy) SFRT can promote tumor immunity via major histocompatibility complex (MHC) up-regulation, antigen presentation, and vascular normalization. (44) At higher doses, SFRT likely retains these immunogenic effects, but also recruits T cells into the tumor and leads to greater direct tumor cell death due to apoptosis or necrosis. (45) Using a B16 mouse melanoma model, Lee et al. showed that SFRT (20 Gy) is more effective than fractionated radiation therapy (FRT; 45 Gy in 3 fractions) in controlling tumors though the total dose of radiation was far less. (45) In their model, the efficacy of SFRT was dependent on CD8 T-cells. Thus, we suspect that 8 Gy x 1 fx could potentially be well tolerated, effective, immunogenic, practical and cost effective regimen to evaluate for the immune-priming effect.

Patients with more than a single symptomatic lesion will be treated to some or all of their lesions, depending on disease burden, necessity for palliation of particular lesions, proximity to other major organs or neurovascular regions, and other patient considerations. There are no anatomic locations that will be deemed inappropriate for RT other than the brain.

Radiation will be delivered using electrons for subcutaneous lesions or rib lesions, and photons using 3D conformal planning and IMRT (intensity modulated radiation treatment) for deeper tumors in the neck, mediastinum, and retroperitoneal regions. None of the patients will be treated with stereotactic radiotherapy techniques. Standard doses of prophylactic antiemetic pre-medications including ondansetron and dexamethasone will be administered if thought to be clinically indicated before treatment of abdominal and retroperitoneal masses

#### ***1.2.1.3 Rationale for Biomarker Research***

The relationship between PD-L1 and responses to PD1 inhibitors is not entirely clear at this time. (46, 47) In patients with NSCLC even though there appears to be an association between PD-L1 expression and response in some trials there has been no association in some trials. (23, 25, 46-50) The discrepancy in the predictive value of the PD-L1 assay are likely related to differences in the definition of positivity, variability of assays across clinical trials and the temporal and spatial heterogeneity of PD-L1. (51, 52) The expression of PD-L1 has also been correlated with the extent of tumor lymphocytic infiltrate. (51, 52) The latter has been observed to be increased after radiation therapy, suggesting one possible mechanism for an improved systemic response after SFRT. (39) We propose here to treat NSCLC patients without regard to PD-L1 expression on biopsies done just prior to initiation of pembrolizumab. When feasible, tissue specimens will be obtained before SFRT and pembrolizumab treatment, and again after SFRT, and local and systemic response will be correlated to expression. The majority of PD-L1 positive tumors were associated with CD4 and CD8 tumor infiltrating lymphocytes (TILs), while the minority of the PD-L1 negative tumors had associated TILs. Moreover, the staining pattern of PD-L1 on melanocytes differed based on proximity to TILs. Interferon- $\gamma$ , a primary inducer of B7-H1 expression, can be detected at the interface of PDL1 positive melanocytes and TILs, possibly reflecting activation of PD-1 on the TILs. This interaction, therefore, might be predictive of antitumor response to PD-1 blockade. Additional mediators of this pathway that might be associated with anti-tumor response, and will be studied on pre-treatment specimens from patients enrolled in this trial. Expression of other members of the B7 super-family of ligands, including PD-L2 and B7-H4 on tumor cells, might be associated with activation of PD-1 on tumor cells.(53, 54) Galectin-9 (the ligand to TIM3), has been proposed as a mediator of PD-1 related T-cell exhaustion. (55) A more sophisticated and accurate predictive biomarker model might be built by incorporating markers on T cells, in addition to quantification of T cell tumor infiltrate. Specifically, co-expression of TIM-3 and PD-1 might be associated with sensitivity to PD-1 blockade.(55) LAG-3 (lymphocyte-activation gene 3) synergizes with PD-1 to inhibit T cell activation.(56, 57) Co-expression of PD-1 and CTLA-4 on T cells is thought to be co-inhibitory, and co-inhibition of these molecules is the basis of ongoing clinical trials. While the T-cell stimulatory role of PD-1H (PD-1 Homologue) on T cells was recently described, its association with anti-tumor response in the setting of PD-1 blockade has yet to be determined. We propose to evaluate several biomarkers studies in collaboration with the Yale Translational Immunology Lab, to characterize the nature of the tumor immune cell populations and several immune evasive pathways including PD-L1 and PD-1. We will use novel quantitative immunofluorescence based assays developed by our collaborators described in earlier publications. (51, 58-62)

Peripheral circulating immune cell phenotyping will be done by Genoptix Inc. In addition, MHC Dextramer® reagents will be used for detection of antigen-specific T cells pre and post CASE 1516

Protocol Amendment 7

06/06/2019

treatment. We will monitor changes of the circulating immune cell population's pre and post treatment and at the time of progression. Novel immune SEQ platforms will be used to interrogate T and B-cell receptor repertoire over time pre-post treatment and at progression. This will identify and define highly expanded clones and diversity of lymphocyte populations.

Correlations between genomic, transcriptomic and proteomic profiles of subjects tumors, and efficacy outcomes will be assessed to identify gene mutations, gene amplifications, RNA-expression levels, and protein-expression levels. Genomic sequencing of tumor cells from tissue relative to non-tumor cells from whole blood will be profiled to identify the genomic variances that may contribute to response or disease progression and provide an understanding of molecular abnormalities. RNA sequencing will be conducted to provide expression data and give relevance to DNA mutations; Quantitative proteomics analysis will be conducted to determine the exact amounts of specific proteins and to confirm expression of genes that are correlative of response and disease progression.

A recent study (NCT01176461) with a mass spectroscopy based serum proteomic assay BDX008 took pre-nivolumab treated melanoma samples from 119 patients. The same assay was independently validated with pre-treatment serum of 30 patients from a non-protocol study using PD-1 blockade regimens. The evaluation showed that patients in the non-protocol study classified as having a high likelihood of good outcome had a 74 percent lower risk of death compared to those with a profile associated with low likelihood of good outcome (hazard ratio [HR] 0.26, p=0.002). Of the 119 patients in the nivolumab trial, those with a profile predicting high likelihood of good outcome had a 50 percent lower risk of disease progression (HR 0.50, p=0.001) and a 62 percent lower risk of death (HR 0.38, p=0.001) compared to those with a profile predicting low likelihood of good outcome. (63) We will evaluate the predictive value of this assay in our trial on all the pre-treatment samples. These studies will be done in collaboration with Biodesix Inc.

An additional potential biomarker of tumor response is cell-free tumor-derived circulating DNA (ctDNA). We will collaborate with BioCept Inc. to develop an ultrasensitive assay for measuring small amounts of cell-free mutant DNA released into the blood from dying tumor cells. The assay covers a broad panel of mutations and uses novel error suppression techniques applied to next-generation sequencing data to enable identification of rare mutant DNA down to a fractional abundance of ~0.02%. Because such ctDNA is highly tumor-specific and is rapidly cleared from the bloodstream, this assay exhibits excellent promise as a quantitative cancer biomarker. Rapid decreases in ctDNA levels have been observed following treatment with surgery, radiation therapy, and systemic therapy (sometimes with an initial spike from tumor kill). Thus, we hypothesize that quantitative changes in ctDNA may provide information that is complementary to radiologic studies for tracking the efficacy of treatment with the PD-1 inhibitor pembrolizumab in patients with non-small cell lung cancer.

We will also evaluate novel quantitative CT imaging algorithms developed in collaboration with the Case Biomedical engineering group to detect tumor inflammation. These imaging based biomarkers could potentially predict tumors with high tumor infiltrating lymphocytes, predict response based on pre-treatment imaging, and also help monitoring patients treated with immunotherapy and potentially help identify early responders and pseudo-progression.

CASE 1516

Protocol Amendment 7

06/06/2019

#### **1.2.1.4 Statistics and Sample Size**

The primary goal of the trial is to assess the RECIST-defined tumor response rate outside the radiation field in previously treated NSCLC patients given radiation to an index lesion followed by pembrolizumab. Secondary goals include assessment of toxicity, other efficacy measures such as progression-free survival, response duration, overall survival, and local control of disease within the radiation field, immune response, and biomarkers such as PD-L1 expression.

In previous studies (KEYNOTE 001 and 010) the ORR to pembrolizumab monotherapy has been approximately 20% in this population. Based on this, an underlying ORR of  $\geq 35\%$  would be considered positive in the current trial whereas a  $\leq 20\%$  ORR would be considered negative. A two-stage accrual design that allows for early stopping due to lack of efficacy will be employed to test this hypothesis. The maximum accrual goal is **48** eligible and evaluable patients. Initially **29** eligible and evaluable patients will be entered into the trial. If  $\leq 6$  patients respond (observed ORR  $\leq 21\%$ ) the trial will be stopped for (relative) lack of efficacy. If more than **6** patients respond an additional **19** eligible and evaluable patients will be entered. Pembrolizumab plus radiation will be considered effective if overall **12** or more patients respond (ORR  $\geq 25\%$ ). With this design the likelihood of stopping the trial early for lack of efficacy is  $\geq 64\%$  if the underlying ORR is  $\leq 20\%$  and  $\leq 7\%$  if it is  $\geq 35\%$ . The overall type I and II errors are **20% and 10%, respectively**.

Safety is an important secondary endpoint. Toxicity will be graded using CTCAE version 4.0 criteria, categorized by organ system, and summarized as frequency counts and percentages. Assuming the trial accrues all **48** patients, the risk of a particular type and/or grade of toxicity will be estimable using an exact 90% confidence interval that has a maximum half-width of **13%**. The likelihood of observing at least one such event is 86% even if the associated risk is only 5%.

Secondary efficacy endpoints such as progression-free survival, response duration, and overall survival will be summarized using the Kaplan-Meier method. Local control will be summarized as a frequency count and percentage. Other endpoints, such as PD-L1 expression, will be summarized as medians and ranges (e.g. proportion of cells expressing PD-L1) or frequency counts and percentages (e.g. number and percent of patient with PD-L1 expression in  $\geq 50\%$  of cells) as appropriate.

Methods such as Fisher's exact test, chi-square tests, logistic regression (categorical data), the logrank test and proportional hazards models (time to event data) will be used to compare patient groups. These analyses are primarily exploratory and it is acknowledged that they will have relatively low statistical power.

All genomic, transcriptomic, and proteomic molecular analyses will be exploratory. These studies would be analyzed using a prospective-retrospective statistical analysis plan (SAP).

## **2 STUDY OBJECTIVES AND ENDPOINTS**

**Hypothesis:** *Focal radiation therapy to tumors can lead to improved tumor antigen presentation in patients with NSCLC. Such treatments could improve tumor responses to pembrolizumab in patients, by enhancing the host immune response.*

### **2.1 Study Objectives**

#### **2.1.1 Primary Objective**

**Objective:** To determine the tumor responses outside the radiation

#### **2.1.2 Secondary Objective**

**Objective:**

1. To determine the progression-free and overall survival in patients with NSCLC receiving pembrolizumab, who receive Single Fraction Radiation Therapy (SFRT)
2. To determine the safety and toxicity of the combination of SFRT and pembrolizumab
3. To examine potential predictive biomarkers in tumor samples and peripheral blood in patients treated with pembrolizumab and SFRT
4. To determine the local control of SFRT in the radiated lesion(s), when SFRT is given with pembrolizumab
5. To evaluate the induction of a T-cell response in patients with metastatic NSCLC treated with radiation and the effect of radiation

#### **2.1.3 Exploratory Objectives**

To examine potential predictive biomarkers in tumor samples and peripheral blood in patients treated with pembrolizumab and SFRT.

### **2.2 Efficacy Endpoints**

#### **2.2.1 Primary Endpoint**

The **Best Overall Response** is the best response recorded from the start of the treatment until disease progression (taking as reference for progressive disease the smallest measurements recorded since the treatment started). The anti-tumor activity will be evaluated as an efficacy endpoints based on radiographic (CT). RECIST 1.1 will be applied for evaluation of tumor response.

#### **2.2.2 Secondary Endpoints:**

1. **Progression Free Survival (PFS)** is defined as the time from initiation of study drug post-SFRT, until the first documented, confirmed progression of disease. PFS will also be measured and report from the initiation of study drug, pre-SFRT.
2. **Overall Survival (OS)** will be measure from the initiation of study therapy
3. Durable Overall Response at 6 months and 12 months
4. **Local Control with SFRT:** The target lesion(s) selected for SFRT will be followed for local control. For the purpose of the study, local control will be defined as a complete response, partial response, or stable disease within the planning target volume. The duration of local control will be measured from the time of SBRT treatment fraction.

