#### 1.1.4 Clinical Trial Data

An open-label phase 1 trial (Keynote 001) was recently published in New England Journal of Medicine, in this large phase I trial side effects, safety, and antitumor activity of pembrolizumab was evaluated in patients with advanced NSCLC. A total of 495 patients received at least one dose of pembrolizumab between May 2012 and February 2014. With a primary objective of safety, side effect profile, and antitumor activity, patients were given intravenous pembrolizumab at a dose of 2 mg or 10 mg per kilogram of body weight every 3 weeks or 10 mg per kilogram every 2 weeks over a 30-minute period.

Overall treatment was well tolerated and the most common treatment related adverse events were fatigue, pruritus, and decreased appetite. Only 9.5% of patients experienced adverse events of grade 3 or higher. Pneumonitis of grade 3 or greater was observed in 9 patients and caused death in one patient.

At the time of the data cutoff, the median duration of follow-up was 10.9 months (range, 5.2 to 27.5), and 115 patients (23.2%) continued to receive treatment. Efficacy data from this study showed an overall response rate of 19.4% (95% confidence interval [CI], 16.0 to 23.2). The response rate was 18.0% (95% CI, 14.4 to 22.2) in the previously treated patients (n=394) and 24.8% (95% CI, 16.7 to 34.3) in the previously untreated patients (n=101). The median duration of response was 12.5 (range, 1.0 to 23.3) months in all patients, 23.2 months (range, 1.0 to 23.3) in previously untreated patients and 10.4 months (range, 1.0 to 10.4) in previously treated patients. Median progression-free survival was 3.7 months (95% CI, 2.9 to 4.1) for all the patients, 3.0 months (95% CI, 2.2 to 4.0) for previously treated patients, and 6.0 months (95% CI, 4.1 to 8.6) for previously untreated patients. Median overall survival was 12.0 months (95%

CI, 9.3 to 14.7) for all patients, 9.3 months (95% CI, 8.4 to 12.4) for previously treated patients, and 16.2 months (95% CI, 16.2 to not reached) for previously untreated patients

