##### 3.1.1 Tumor Imaging and Assessment of Disease

The initial tumor imaging will be performed within 30 days prior to the first dose of trial treatment. CT scans are the required modality for measurable disease unless a subject has a clinical condition e.g. severe contrast allergy, or the lesions are significantly better visualized through the use of an MRI. The same imaging technique must be used for a subject throughout the study. Scans performed as part of routine clinical management are acceptable for use as the screening scan if they are of diagnostic quality and performed within 30 days prior to the first dose of trial treatment. Repeat imaging would be performed after every 2 cycles of therapy for the remainder of the on-study treatment period or more frequently if clinically indicated. CT timing should follow calendar days and should not be adjusted for delays in cycle starts or extension of pembrolizumab cycle frequencies. This protocol recommends that patients receiving pembrolizumab as standard of care after EOT will have CT scans every 9 weeks +/- 14 days until the subject experiences confirmed disease progression or starts a new antineoplastic therapy.

Subjects who discontinue trial treatment for reasons other than disease progression should also receive tumor imaging every 9 weeks +/- 14 days until the subject experiences confirmed disease progression or starts a new antineoplastic therapy.

Disease progression for trial eligibility will be according to RECIST 1.1 criteria. Local reading (investigator assessment with site radiology reading) will be used to determine eligibility and for subject management. De-identified imaging will also be obtained from all participating sites for

imaging correlative studies to be done by collaborators at Case Western Reserve University Biomedical Engineering group.

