#### **6.2.1.1 *SFRT Planning***

Patients will undergo CT simulation and treatment planning per standard practice. Patient immobilization should be sufficient to ensure minimal intra- and inter-fraction set-up error, and is otherwise left to the discretion of the treating radiation oncologist. The treating physician will define a planning target volume (PTV) to which the dose will be described, and which will be used to define local control or local failure. 3D conformal beam arrangement is encouraged, though advanced techniques are allowed at the discretion of the treating radiation oncologist. At least 90% of the PTV should receive 90% or more the prescription dose. All organs at risk within 5 cm of the PTV will be contoured, and dose-volume histograms produced. For the treatment dose of 8 Gy x 1 in a non-Previously irradiated field it is not expected that normal tissue dose-limits would be exceeded, however, the treatment field should be evaluated at the discretion of the treating radiation oncologist.

This will be followed by pembrolizumab 200mg solution intravenously every 3 weeks until progression of disease (PD) (RECIST) or unacceptable toxicity (protocol defined). Treatment cycles will be every 21 days, and formal radiographic assessment will be performed at baseline and then after every 2 cycles i.e. end of C2, C4, etc. Tumor measurements will be performed according to RECIST criteria.

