### **6.9 Withdrawal/Discontinuation**

Subjects may withdraw consent at any time for any reason or be dropped from the trial at the discretion of the investigator should any untoward effect occur. In addition, a subject may be withdrawn by the investigator or the Sponsor if enrollment into the trial is inappropriate, the trial plan is violated, or for administrative and/or other safety reasons. When a subject discontinues/withdraws prior to trial completion, all applicable activities scheduled for the final trial visit should be performed at the time of discontinuation. Any adverse events which are present at the time of discontinuation/withdrawal should be followed in accordance with the safety requirements outlined in Section 7.2 - Assessing and Recording Adverse Events. Subjects who a) attain a CR or b) complete 24 weeks of treatment with pembrolizumab may discontinue treatment with the option of restarting treatment if they meet the criteria specified in Section 6.9.1. After discontinuing treatment following assessment of CR, these subjects should return to the site for a Safety Follow-up Visit (described in Section 6.3.1) and then proceed to the Follow-Up Period of the study (described in Section 6.3.1.1).

A subject must be discontinued from the trial for any of the following reasons:

- The subject or legal representative (such as a parent or legal guardian) withdraws consent.
- Confirmed radiographic disease progression

*Note: A subject may be granted an exception to continue on treatment with confirmed radiographic progression if clinically stable or clinically improved.*

CASE 1516

Protocol Amendment 7

06/06/2019

- Unacceptable adverse experiences as described in Section Intercurrent illness that prevents further administration of treatment
- Investigator's decision to withdraw the subject
- The subject has a confirmed positive serum pregnancy test
- Noncompliance with trial treatment or procedure requirements
- The subject is lost to follow-up
- Administrative reasons

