The End of Treatment and Follow-up visit procedures are listed in Section 6.2.2 (Treatment Regimen Overview). After the end of study treatment, each subject will be followed for 30 days for adverse event monitoring. Subjects who discontinue study treatment for reasons other than progressive disease will have post-treatment follow-up visits for disease status every 9 weeks +/- 14 days until disease progression, initiating a non-study cancer treatment, withdrawing consent, or becoming lost to follow-up. Additionally, subjects who continue to receive pembrolizumab as standard of care will be followed for disease status every 9 weeks +/- 14 days until disease progression, initiating a non-study cancer treatment, withdrawing consent, or becoming lost to follow-up. After documented disease progression or initiation of a non-study cancer treatment, each subject will be followed by telephone for overall survival until death, withdrawal of consent, or the end of the study, whichever occurs first.

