Secondary efficacy endpoints such as progression-free survival, response duration, and overall survival will be summarized using the Kaplan-Meier method. Local control will be summarized as a frequency count and percentage. Other endpoints, such as PD-L1 expression, will be summarized as medians and ranges (e.g. proportion of cells expressing PD-L1) or frequency counts and percentages (e.g. number and percent of patient with PD-L1 expression in  $>50\%$  of cells) as appropriate.

Methods such as Fisher's exact test, chi-square tests, logistic regression (categorical data), the logrank test and proportional hazards models (time to event data) will be used to compare patient groups. These analyses are primarily exploratory and it is acknowledged that they will have relatively low statistical power.

All genomic, transcriptomic, and proteomic molecular analyses will be exploratory. These studies would be analyzed using a prospective-retrospective statistical analysis plan (SAP).

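### PFS as defined leaves out death, so the Kaplan-Meier curve would show time to progression under a PFS label

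*Combined protocol and SAP*

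**What the plan says.** PFS is part of the first secondary objective (Section 2.1.2). Section 2.2.2 says that it "is defined as the time from initiation of study drug post-SFRT, until the first documented, confirmed progression of disease". It then adds a second version: "PFS will also be measured and report from the initiation of study drug, pre-SFRT". The second version changes the time origin and adds no event.

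The analysis text, the same in Sections 1.2.1.4 and 8, reads: "Secondary efficacy endpoints such as progression-free survival, response duration, and overall survival will be summarized using the Kaplan-Meier method". Neither section says which events count or how patients are censored, and the subset analyses in Section 8.1 add nothing on this. Section 11.2 cites RECIST 1.1 for assessing tumour response, not to define PFS.

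On follow-up, Section 3.1.1 schedules imaging off study treatment "until the subject experiences confirmed disease progression or starts a new antineoplastic therapy". Section 6.9 lists "Confirmed radiographic disease progression" as a reason for discontinuation, and says of later follow-up: "After documented disease progression or initiation of a non-study cancer treatment, each subject will be followed by telephone for overall survival until death". Section 6.3.1.1 follows survival status every 12 weeks for up to 5 years.

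**The concern.** The name of the endpoint implies that death counts. The written definition says otherwise, and nothing else in the document corrects it. An analyst who follows the definition and one who follows the name would draw different curves from the same data, and the plan does not choose between them in advance.

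The literal reading also tends to flatter the treatment. Censoring a death treats that patient as if he or she would have gone on with the same progression risk as the survivors. In a single-arm trial, the natural use of PFS is to set it beside published pembrolizumab results such as the one in Section 1.1.4: "Median progression-free survival was 3.7 months (95% CI, 2.9 to 4.1) for all the patients". A time-to-progression curve labelled PFS would tend to look better in that comparison.

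Two smaller gaps sit in the same sentences:

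- **Confirmation.** Sections 2.2.2, 3.1.1 and 6.9 call progression *confirmed* without saying what confirms it. Section 6.2.1.1 and the follow-up text of Section 6.9 refer to progression without that word. If a second scan is required, a patient who dies after a first, unconfirmed progression also has no event.
- **The pre-SFRT origin.** It does not fit Section 3.4, Table 2 or note a of Section 6.4, all of which place SFRT before pembrolizumab or on the same day. This is a matter of wording.

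**Working it through.** The plan states no PFS target, event count or power, so there is no figure of its own to reproduce.

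**Direction.** At each event time let *n* patients be at risk, *d* progress and *c* die without progression. With deaths counted, the Kaplan-Meier factor is 1 − (d + c)/n. With deaths censored on the day of death, the risk sets are the same and the factor is 1 − d/n, which is never smaller. The second curve is therefore at or above true PFS at every time. If deaths are censored at the last scan instead, those patients leave the risk set earlier, *n* shrinks, and this ordering is no longer guaranteed. The text fixes neither date.

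**Size, closed form.** Inputs:

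- Median *m* = 3.7 months for all patients, or 3.0 months for previously treated patients (both from Section 1.1.4). Each is taken as death-inclusive, which that section does not state.
- Share *f* of first events that are deaths: assumed 10%, 20% or 30%; the documents give none.
- Constant, independent hazards: assumed.

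The PFS hazard is ln 2/m. With deaths censored, the curve estimates (1 − f) ln 2/m. The reported median is then m/(1 − f), and the six-month value is 2^(−6(1 − f)/m).

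| f | Median, m = 3.7 | Six months, m = 3.7 | Median, m = 3.0 | Six months, m = 3.0 |
|---|---|---|---|---|
| 0 (true PFS) | 3.7 | 32.5% | 3.0 | 25.0% |
| 10% | 3.7/0.9 = 4.11 | 36.4% | 3.33 | 28.7% |
| 20% | 3.7/0.8 = 4.62 | 40.7% | 3.75 | 33.0% |
| 30% | 3.7/0.7 = 5.29 | 45.5% | 4.29 | 37.9% |

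**Size with scheduled scans.** This was simulated with 2,000 trials of 48 patients per share, m = 3.7 and 24 months of follow-up. Scans fell at weeks 6, 12, 18 and 24 (±7 days), then every 9 weeks (±14 days). Progression was dated at the next scan, and under the last-scan rule a death before any scan was censored at day 0. On average 5.4, 10.6 and 15.8 of 48 patients died without documented progression. Mean six-month estimates:

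| f | Deaths counted | Censored at death | Censored at last scan |
|---|---|---|---|
| 10% | 35.3% | 39.6% | 39.0% |
| 20% | 34.9% | 43.7% | 42.6% |
| 30% | 34.6% | 48.5% | 46.9% |

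The overstatement is 4.3, 8.8 and 13.9 points with censoring at death, and 3.7, 7.7 and 12.3 points with censoring at the last scan. The last-scan curve fell below the deaths-counted curve at some time point in 35.8%, 15.4% and 8.5% of trials, but at six months in only 1.3%, 0.1% and 0.0%. Its median was shorter in none of the 6,000 trials. I put no weight on the simulated medians themselves, because at the 10% share the median falls in the gap between the week 18 and week 24 scans.

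**The case against.** The best reply is that the name itself says *survival*, no sentence says that deaths are censored, and a sensible analyst would count them. On this view the fault is a drafting slip in a descriptive endpoint with no hypothesis test. Deaths are not lost either, since overall survival is reported separately.

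The point about weight stands: nothing in the primary design depends on PFS. The point about intent does not remove the problem. The protocol wrote out an explicit definition, and that definition conflicts with the label.

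The illustration can also be challenged, and three of those challenges are fair:

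- **Death shares.** They have no source in the documents.
- **Scan schedule.** The week 24 scan follows the every-two-cycles text (Sections 3.1.1, 6.2.1.1 and 6.4 note c), but Table 3 marks on-treatment imaging only at cycles 3, 5 and 7. With the Table 3 scans alone and then every 9 weeks, six-month PFS with deaths counted is 41.2%, 40.1% and 39.3%, and with censoring at death 46.2%, 50.3% and 55.1%. The gaps become 5.0, 10.2 and 15.8 points, slightly larger. At the 10% share, however, the schedule moves the level (41.2 − 35.3 = 5.9 points) more than the missing deaths do (4.3 points).
- **Reference median.** Section 8 describes previously treated patients, for whom Section 1.1.4 gives 3.0 months. The levels then fall, but the six-month gaps barely change.

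So the levels depend on the assumptions, while the direction is the same in every version. It can also be argued that *confirmed* means no more than shown on imaging. That is possible, but the text does not say so.

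**Conclusion.** The concern holds. The only PFS definition excludes death, and no other section restores it, so following the plan literally gives time to progression under a PFS label. With censoring at the death date the upward direction is an algebraic fact. With censoring at the last scan it is usual but not guaranteed at every time point.

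The size cannot be known from the documents. For death shares of 10% to 30%, a constant-hazard illustration lengthens the median by a factor of 1/(1 − f), that is by 11% to 43%. With scheduled scans it raises the six-month estimate by roughly 4 to 16 points across the censoring rules and schedules tried.

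This should be fixed, but it does not threaten the trial: 48 patients, the stage-one stopping rule and the success criterion all rest on response.

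**What to change.** In Sections 2.2.2 and 8:

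- Define PFS as time from the first pembrolizumab dose to the first of RECIST 1.1 progression or death from any cause, and censor event-free patients at their last tumour assessment. If time to progression is what is wanted, rename the endpoint and say how deaths are handled.
- State whether confirmation is required for the endpoint and, if so, what confirms it. Date the event at the first scan that shows progression.
- Give one analysis rule for new anticancer therapy started before progression. Protocol imaging ends at that point, so a sensitivity analysis that follows patients further would rest on deaths and any routine scans that happen to exist.
- Reconcile the pre-SFRT origin with Section 3.4, Table 2 and note a of Section 6.4.

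The cost is a few sentences. Scan dates up to progression or new therapy (Sections 3.1.1 and 6.9), and survival status and later treatments (Section 6.3.1.1), are already collected, so no extra imaging or visits are needed. The reported PFS may be slightly less favourable. The decision on confirmation changes which scans count as events, so it should be made before the data are analysed.
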